1.3 Schedule of Activities, Table 3: Schedule of Activities: Extension Treatment Period Week 100 Through Week 248	 Added endoscopy assessment at Weeks 144, 192, 240, and ED. Liver function tests replaced with hematology and chemistry assessments. 	
4.1 Overall design	Endoscopy added to safety assessments.	

1. PROTOCOL SUMMARY

1.1. Synopsis

A Phase 3, Randomized, Double-blind, Placebo-controlled, Parallel-group, Multicenter Study to Evaluate the Efficacy and Safety of Guselkumab Subcutaneous Induction Therapy in Participants with Moderately to Severely Active Ulcerative Colitis

IND: 140330

EU Trial Number: 2023-504719-34

A Phase 3 Study to Evaluate the Efficacy and Safety of Guselkumab Subcutaneous Induction Therapy in Participants with Moderately to Severely Active Ulcerative Colitis

DESCRIPTION OF COMPOUND

Guselkumab is a fully human immunoglobulin G1 lambda monoclonal antibody that binds to human IL-23 with high specificity and affinity. The binding of guselkumab to IL-23 blocks the binding of extracellular IL-23 to the cell surface IL-23 receptor, inhibiting IL-23 mediated intracellular signaling, activation and cytokine production.

The term "study intervention" throughout the protocol, refers to study drug.

BENEFIT-RISK ASSESSMENT

Guselkumab, an IL-23 antagonist, has a well-defined long-term safety profile and has been extensively studied in the approved indications. Taking into account the measures taken to minimize risk to participants in this study, the potential risks identified in association with guselkumab are justified by the anticipated benefits that may be provided to participants with moderately to severely active UC. More detailed information about the known and expected benefits and risks of guselkumab may be found in the IB.

OBJECTIVES AND ENDPOINTS

The primary and secondary objectives and endpoints are listed below.

Objectives	Endpoints
Primary	
To evaluate the efficacy, including clinical remission, of guselkumab SC induction compared to placebo in participants with moderately to severely active UC	• Clinical remission at Week 12 (defined as a CCI and not increased from baseline, a rectal bleeding subscore of 0, and an CCI with no friability present on the endoscopy)
Secondary	
To further evaluate the efficacy of guselkumab SC induction compared to placebo across a range of outcome measures	• Symptomatic remission at Week 12 (defined as a CCI and not increased from baseline, and a rectal bleeding subscore of 0)
	• Endoscopic improvement at Week 12 (defined as an endoscopy

Objectives	Endpoints
	subscore of 0 or 1 with no friability present on the endoscopy)
	• Clinical response at Week 12 (defined as a decrease from induction baseline in the CCI by ≥30% and ≥2 points, with either a ≥1-point decrease from baseline in the rectal bleeding subscore or a rectal bleeding subscore of 0 or 1)
	Clinical remission at Week 24
	Symptomatic remission at Week 24
	• Endoscopic improvement at Week 24
	Clinical response at Week 24
	Histologic-endoscopic mucosal improvement at Week 12 (defined as a combination of histologic improvement [neutrophil infiltration in <5% of crypts, no crypt destruction, and no erosions, ulcerations or granulation tissue according to the column and endoscopic improvement as defined above)
To evaluate the safety of guselkumab SC induction compared to placebo	• Frequency and type of AEs (including SAEs)

HYPOTHESIS

The primary hypothesis of this study is that guselkumab SC induction is superior to placebo SC in achieving clinical remission at Week 12 among participants with moderately to severely active UC.

OVERALL DESIGN

This is a randomized, double-blind, placebo-controlled, parallel-group, multicenter study to evaluate the efficacy and safety of guselkumab SC induction therapy in adult participants with moderately to severely active UC who have demonstrated an inadequate response to or intolerance of conventional (ie, 6-MP, AZA, or corticosteroids) or advanced therapy (ADT; ie, TNF α antagonists, vedolizumab, ozanimod, or approved JAK inhibitors).

The main treatment period will evaluate guselkumab SC treatment through 24 weeks of therapy. Starting at Week 12, all participants who were taking corticosteroids at Week 0 must begin tapering their corticosteroid dose. This tapering is mandatory, unless not medically feasible. All participants who reach the Week 24 visit and are benefiting from study intervention in the opinion of the investigator are eligible for the study extension with treatment up to Week 248. At Week 24, participants entering the extension period will continue the same treatment regimen they were receiving prior to Week 24. The study will be unblinded after the last participant completes the Week 48 assessments and the Week 48 DBL and analyses

occur. Upon study unblinding, placebo participants who have not been rescued with guselkumab will be discontinued from study intervention and have a safety follow-up visit. All other participants will continue on guselkumab treatment up to Week 248.

Efficacy, safety, PK, immunogenicity, and biomarkers will be assessed according to the SoA.

Participants will complete an ED visit upon discontinuation of study intervention and before termination of study participation. All randomized and treated participants are to complete the safety follow-up visit 12 weeks after the last dose of study intervention.

Database locks are planned for Week 24, Week 48, and when the last participant completes the last scheduled assessment as shown in the SoA. Additional DBLs may be added as necessary.

End of Study

The end of study is considered as the last scheduled study assessment shown in the Schedule of Activities for the last participant in the study or if a decision has been made by the sponsor not to pursue an indication in UC or SC induction and appropriate follow-up has been completed. The final data from the study site will be sent to the sponsor (or designee) after completion of the final participant assessment at that study site, in the time frame specified in the Clinical Trial Agreement.

NUMBER OF PARTICIPANTS

The target sample size is 399 participants, with 133 participants per intervention group. Participants who have demonstrated an inadequate response to or intolerance of advanced therapy (ADT-IR) will comprise approximately 40% to 50% of the population.

INTERVENTION GROUPS AND DURATION

The overall study duration is up to 268 weeks. The study comprises of the following periods

- Screening period: up to 8 weeks
- Main treatment period: 24 weeks
- Extension treatment period: 224 weeks
- Safety Follow-up period: until approximately 12 weeks after the last dose of study intervention.

At Week 0, eligible participants will be randomly assigned in a 1:1:1 ratio to one of the following SC treatments:

- 133 participants to guselkumab CCI at Weeks 0, 4, and 8 followed by guselkumab 200 mg SC q4w through Week 24
- 133 participants to guselkumab CCl at Weeks 0, 4, and 8 followed by guselkumab 100 mg SC q8w through Week 24
- 133 participants to placebo SC q4w from Week 0 through Week 24

Participants will be allocated to an intervention group using permuted block randomization stratified by ADT-IR status (Yes/No) and CCI at baseline (moderate [2] or severe [3]) obtained during central review of the video endoscopy.

All participants in the placebo group who meet rescue criteria at Week 16 will receive rescue treatment, ie, guselkumab CC at Weeks 16, 20, and 24 followed by guselkumab 100 mg SC q8w. Participants

randomized to guselkumab who meet rescue criteria at Week 16 will continue their assigned treatment regimen and receive blinded sham rescue with matching placebo SC injections at Weeks 16, 20, and 24.

Description of Interventions

Participants will receive the study interventions as described above in the Intervention Groups and Duration section.

Guselkumab will be provided in 2 dose strengths: guselkumab CCI in a single-dose PFS-Y and in a single-dose PFS-U. Matching placebo will be provided as CCI in a single-dose PFS-Y and as CCI in a single-dose PFS-U.

EFFICACY EVALUATIONS

Efficacy evaluations will include the following:

- CCI
- Inflammatory PD markers including CRP and fecal calprotectin
- Histological assessments (eg, CC)
- Patient-reported outcome measures to assess CCI outcomes, fatigue, and UC symptoms and signs (ie, CCI

PHARMACOKINETIC EVALUATIONS

Serum samples will be analyzed to determine concentrations of guselkumab using validated, specific and sensitive immunoassay methods by or under the supervision of the sponsor.

IMMUNOGENICITY EVALUATIONS

Serum samples will be screened for antibodies binding to guselkumab and the titer of confirmed positive samples will be reported. Other analyses may be performed to verify the stability of antibodies to guselkumab and/or further characterize the immunogenicity of guselkumab.

PHARMACODYNAMIC AND BIOMARKER EVALUATIONS

Biomarker assessments will be made to examine the biologic response to treatment and to identify biomarkers that are relevant to guselkumab treatment and/or ulcerative colitis. Assessments will include the evaluation of relevant biomarkers in serum, whole blood, and endoscopic biopsy samples, where local regulations permit.

SAFETY EVALUATIONS

Safety assessments include AEs, clinical laboratory tests, vital signs and physical examinations, a screening electrocardiogram, suicidality assessment, concomitant medication review, monitoring for injection-site reactions and hypersensitivity reactions, a tuberculosis evaluation and other infection assessments.

STATISTICAL METHODS

Sample Size Determination

Sample size was determined by the power to detect significant differences in the primary endpoint of clinical remission at Week 12, and by the objective of maintaining at least 85% power across secondary endpoints at Week 12 between the combined guselkumab SC induction groups and the placebo SC group and secondary endpoints at Week 24 between each guselkumab group and the placebo group, using 2-sided

chi-square tests with significance level 0.05. The assumed rates are 22% versus 8% (guselkumab vs placebo) for clinical remission at Week 12. The study is sized such that the guselkumab therapy achieves a >95% power for the primary endpoint and a $\geq 85\%$ power for all secondary endpoints.

Efficacy Analyses

Descriptive statistics (eg, mean, median, SD, IQ range, minimum, and maximum) will be used to summarize continuous variables. Counts and percentages will be used to summarize categorical variables. Graphical data displays (eg, line plots) may also be used to summarize data.

Analyses suitable for categorical data (eg, chi-square tests, CMH tests, or logistic regression, as appropriate) will be used to compare the proportions of participants achieving selected endpoints (eg, clinical response). In cases of rare events, the Fisher's exact test will be used for treatment comparisons. Continuous response parameters measured at more than one post-baseline visit will be compared using an MMRM model (unless otherwise specified). If the normality assumption is in question, an appropriate transformation may be implemented before fitting the MMRM model. Continuous response parameters measured at only one post-baseline visit will be compared using a ANOVA or ANCOVA, unless otherwise specified. In cases of small sample size, t-test will be used for treatment comparisons.

Efficacy analyses will be based on all randomized participants who received at least 1 dose of study intervention (the Full Analysis Set). Participants will be analyzed according to the treatment group to which they were randomized regardless of the treatment they received.

The primary endpoint (clinical remission at Week 12) will be analyzed based on the primary estimand, considering treatment groups, population, variable, ICE strategies, and population-level summary. After accounting for the ICEs, any participants who are missing any or all of the 3 subscores that comprise the primary endpoint at Week 12 will be considered not to be in clinical remission at Week 12 (ie, nonresponder imputation).

Summaries of the proportion of participants in clinical remission at Week 12 will be presented by treatment group. The common risk difference and the associated 95% confidence interval between the combined guselkumab SC induction group and the placebo group will be computed by use of Mantel-Haenszel stratum weights and the Sato variance estimator. The primary endpoint will be tested by a two-sided Mantel-Haenszel test for the common risk difference. Stratification will be by the ADT-IR status (Yes/No), and CCI at baseline (moderate [2], severe [3]) as obtained during central review of the video endoscopy. The study will be considered successful if the test for the primary endpoint is positive. While a multiplicity-controlled testing procedure will be implemented to control for the type I error rate at the 0.05 significance level (2-sided) across the primary and secondary endpoints, the primary endpoint will be tested at full significance level. Only if this test is significant, secondary endpoints will be tested in a confirmatory manner.

Safety Analyses

Safety data, including but not limited to, AEs, SAEs, infections, injection-site reactions, changes in laboratory parameters (hematology and chemistry), and suicidal ideation and behavior will be summarized. All reported AEs will be included in the analysis.

Other Analyses

Patient-reported Outcomes

Analysis of patient-reported outcomes will follow the general considerations. The testing of these endpoints will not be controlled for multiplicity and nominal p-values will be provided.

Pharmacokinetic Analyses

Serum guselkumab concentration over time will be summarized for each treatment group using descriptive statistics. Population PK modeling may be conducted when appropriate. If the population PK analysis are conducted, the results of these analysis will be presented in a separate report.

Pharmacokinetic/Pharmacodynamic Analyses

The relationship between serum guselkumab concentrations and efficacy measures will be analyzed graphically. If feasible, a suitable exposure-response model may be developed to describe the relationship between serum guselkumab exposure and efficacy. Results of the population PK/PD analysis will be presented in a separate technical report.

Immunogenicity Analyses

The incidence of antibodies to guselkumab will be summarized for all participants in the immunogenicity analysis set.

A listing of participants who are positive for antibodies to guselkumab will be provided. The maximum titers of antibodies to guselkumab will be summarized for participants who are positive for antibodies to guselkumab.

[figure not shown]
The incidence of neutralizing antibodies to guselkumab will be summarized for participants who are positive for antibodies to guselkumab and have samples evaluable for neutralizing antibodies to guselkumab.

Biomarker Analyses

Changes in serum protein analytes, whole blood RNA, and colonic biopsy RNA obtained over time (where local regulations permit) will be summarized by treatment group. Associations between baseline levels and changes from baseline in select biomarkers and response to treatment will be explored.

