9.2. Sample Size Determination

Sample size was determined by the power to detect significant differences in the primary endpoint of clinical remission at Week 12, and by the objective of maintaining at least 85% power across secondary endpoints at Week 12 between the combined guselkumab SC induction groups and the placebo SC group as well as for secondary endpoints at Week 24 between each guselkumab group and the placebo group, using 2-sided chi-square tests with significance level 0.05. Combination of guselkumab SC induction groups for the primary endpoint and other Week 12 endpoints is warranted by the fact their treatment is identical through the induction period, and only differs after assessment of the primary endpoint at Week 12.

With assumed clinical remission rates of 8% for placebo and 22% for the combined guselkumab groups (based on data from Phase 2b guselkumab UC IV induction study [CNTO1959UCO3001]) and Phase 3 ustekinumab UC program [CNTO1275UCO3001], a total of 399 participants (randomized 1:1:1 for guselkumab CCI q4w (Weeks 0, 4, and 8) followed by guselkumab 200 mg SC q4w: guselkumab GCI q4w (Weeks 0, 4, and 8) followed by guselkumab 100 mg SC q8w: Placebo, yielding a 2:1 guselkumab:placebo randomization ratio for Week 12 comparisons) will ensure >95% power for the primary endpoint. This sample size also protects against a slightly lower remission rate of 20% for the combined guselkumab groups or a slightly

higher remission rate of 9.5% in the placebo group (as observed in CNTO1959UCO3001), yielding a power of 90% in both cases.

Individual power values (ie, without consideration of an adjustment for multiplicity) achieved for secondary endpoints at Week 12 are described in Table 5.

Table 5: Power for Secondary Endpoints at Week 12 with a Total of 399 Participants (2:1 Guselkumab:Placebo)

Endpoints	Proportion achieving endpoint in Placebo group	Proportion achieving endpoint in combined Guselkumab group	Power
Symptomatic remission	20%	45%	>99%
Endoscopic improvement	13%	28%	94%
Clinical response	30%	60%	>99%
Histologic-endoscopic mucosal improvement	8%	19%	85%
Assumed rates were based ustekinumab UC program	on data from Phase 2b guse	lkumab UC IV induction study and	Phase 3

For the secondary endpoints at Week 24, power is determined by the pairwise comparison of individual guselkumab groups to placebo (see Table 6).

Table 6: Power for Secondary Endpoints at Week 24 with a Total of 399 Participants (133 per Treatment Group)

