9.4.3.2. Confirmatory Testing Procedure

A multiple testing procedure is planned to control the overall Type 1 error rate in the study at the 2-sided 0.05 significance level. The planned procedure is depicted in Figure 3. It follows a fixed sequence approach, where the primary endpoint and the Week 12 secondary endpoints (with the exception of histologic-endoscopic mucosal improvement) for the combined guselkumab groups vs placebo are tested prior to the secondary endpoints at Week 24. For the Week 24 endpoints, the testing sequence continues with testing all 4 endpoints in the guselkumab CCI q4w (Weeks 0, 4, and 8) followed by guselkumab 200 mg SC q4w group against placebo and then testing all 4 endpoints in the guselkumab GCI q4w (Weeks 0, 4, and 8) followed by guselkumab 100 mg SC q8w group against placebo. Histologic-endoscopic mucosal improvement at Week 12 is the last element of the testing sequence and is tested for the combined guselkumab groups against placebo.

This testing procedure may be revised prior to Week 24 database lock and unblinding if warranted by emerging external data. For example, the position of testing individual guselkumab groups against placebo may be changed based on QUASAR (CNTO1959UCO3001) maintenance data, which are expected to become available prior to any data unblinding in this study. Any such changes will be documented in the SAP. No changes to the testing procedure based on CNTO1959UCO3004 (this study) results will be made.

[figure not shown]

Figure 3: Multiple Testing Procedure for Primary and Secondary Endpoints

Note 1: All p-values are 2-sided

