3. SAMPLE SIZE DETERMINATION

Sample size was determined by the power to detect significant differences in the primary endpoint of clinical remission at Week 12, and by the objective of maintaining at least 85% power across secondary endpoints at Week 12 between the combined guselkumab SC induction groups and the placebo SC group as well as for symptomatic remission at Week 24 between each guselkumab group and the placebo group, using 2-sided χ^2 tests with significance level 0.05. Combination of guselkumab SC induction groups for the primary endpoint and other Week 12 endpoints is warranted by the fact their treatment is identical through the induction period, and only differs after assessment of the primary endpoint at Week 12.

With assumed clinical remission rates of 8% for placebo and 22% for the combined guselkumab groups (based on data from Phase 2b guselkumab UC IV induction study [CNTO1959UCO3001] and Phase 3 ustekinumab UC program [CNTO1275UCO3001]), a total of 399 participants (randomized 1:1:1 for guselkumab CC q4w [Weeks 0, 4, and 8] followed by guselkumab 200 mg SC q4w: guselkumab q4w [Weeks 0, 4, and 8] followed by guselkumab 100

mg SC q8w: Placebo, yielding a 2:1 guselkumab:placebo randomization ratio for Week 12 comparisons) will ensure >95% power for the primary endpoint. This sample size also protects against a slightly lower remission rate of 20% for the combined guselkumab groups or a slightly higher remission rate of 9.5% in the placebo group (as observed in CNTO1959UCO3001), yielding a power of 90% in both cases.

Individual power values (ie, without consideration of an adjustment for multiplicity) achieved for secondary endpoints at Week 12 with a total of 399 participants (2:1 guselkumab:placebo) are described in Table 2.

Table 2: Power for Secondary Endpoints at Week 12

Endpoints	Proportion achieving endpoint in Placebo group	Proportion achieving endpoint in combined Guselkumab group	Power
Symptomatic remission	20%	45%	>99%
Endoscopic improvement	13%	28%	94%
Clinical response	30%	60%	>99%
Histologic-endoscopic mucosal improvement	8%	19%	85%
Assumed rates were based on data from the Phase 2b guselkumab UC IV induction study and the Phase 3 ustekinumab UC program			

For the secondary endpoints at Week 24, power is determined by the pairwise comparison of individual guselkumab groups to placebo (see Table 3).

Table 3: Power for Secondary Endpoints at Week 24 with a Total of 399 Participants (133 per Treatment Group)

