5.3. Primary Endpoint Analysis

5.3.1. Definition of Endpoint

[figure not shown]
The primary endpoint is clinical remission at Week 12.

Clinical remission is defined as a stool frequency subscore of 0 or 1 and not increased from baseline, a rectal bleeding subscore of 0, and an endoscopy subscore of 0 or 1 with no friability present on the endoscopy.

The above definition is based on Mayo score components as described below.

5.3.2. **Estimands**

An estimand is a precise definition of the primary targeted intervention effect defined by the following 5 attributes: study intervention by Week 12, population, variable (endpoint), intercurrent events (ICEs) and corresponding strategies, and population-level summary.

Primary Trial Objective: To evaluate the efficacy of guselkumab SC at Week 12 compared with placebo SC.

Estimand Scientific Question of Interest: What difference in proportions of patients considered to experience benefit from treatment by Week 12 (according to the responder criteria for clinical remission used in the estimand variable definition) can be expected under the assignment to either guselkumab or placebo?

5.3.2.1. **Primary Estimand (Estimand 1)**

The primary estimand (i.e., a precise definition of the primary targeted treatment effect) is defined by the following 5 attributes:

i) Treatment by Week 12:

Experimental: Combined guselkumab induction dose group (i.e., both guselkumab groups who received at Weeks 0, 4, and 8; see Section 1.2)

CONFIDENTIAL – FOIA Exemptions Apply in U.S.

Control: Placebo SC q4w (Weeks 0, 4, 8)

- **ii) Population**: Participants with moderately to severely active ulcerative colitis as reflected in the inclusion/exclusion criteria.
- **iii)** Variable (Endpoint): A binary response variable (response/nonresponse) where response is defined as achieving a stool frequency subscore of 0 or 1 and not increased from baseline, a rectal bleeding subscore of 0, and an endoscopy subscore of 0 or 1 with no friability present on the endoscopy at Week 12 and none of the ICEs in categories 1 to 4 and 6 outlined in Table 6 has occurred prior to the Week 12 visit.
- iv) Intercurrent Events and Corresponding Strategies: ICEs and the corresponding analysis strategies are defined in Table 6.

Table 6: Intercurrent Events and Respective Analysis Strategies

ICE	Analysis strategy for ICE
1. An ostomy or colectomy (partial or total)	Composite strategy: Occurrence of these ICEs will be

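### Does the synopsis overstate secondary power by quoting at least 85% without allowing for the fixed testing sequence?

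*Protocol*

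**What the plan says.** The synopsis bases the sample size on two-sided chi-square tests at 0.05, with the combined guselkumab groups against placebo at Week 12 and each group against placebo at Week 24. It then concludes that the study "achieves a >95% power for the primary endpoint and a $\geq 85\%$ power for all secondary endpoints".

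Protocol Section 9.2 qualifies the Week 12 figures: "Individual power values (ie, without consideration of an adjustment for multiplicity) achieved for secondary endpoints at Week 12 are described in Table 5". That table includes histologic-endoscopic mucosal improvement at 85%. The Week 24 sentence is shorter: "For the secondary endpoints at Week 24, power is determined by the pairwise comparison of individual guselkumab groups to placebo (see Table 6"). SAP Section 3 has the same Week 12 caveat and the same short Week 24 sentence. Its stated sizing objective at Week 24 is narrower than the protocol's, "as well as for symptomatic remission at Week 24 between each guselkumab group and the placebo group", although SAP Table 3 lists four Week 24 endpoints.

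Protocol Section 9.4.3.2 and SAP Section 5.4.2.2 fix the order of testing: the primary endpoint, three Week 12 endpoints, four q4w Week 24 endpoints, four q8w Week 24 endpoints, then one final endpoint (1 + 3 + 4 + 4 + 1 = 13 steps). The q4w block comes first: "followed by guselkumab 200 mg SC q4w group against placebo and then testing all 4 endpoints in the guselkumab" arm with q8w maintenance. "Histologic-endoscopic mucosal improvement at Week 12 is the last element of the testing sequence".

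**The concern.** In a fixed sequence, a claim is confirmed only if its own test and every earlier test are significant. Each step keeps the full 0.05, but the chance of confirming a late claim is lower than the power of its test alone.

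The synopsis sentence does not say which kind of power it means. A reader could take 85% as the smallest chance that any secondary claim is confirmed. If that were the meaning, the statement would be too favourable for the q8w arm and for the last endpoint, and an untested or non-significant late result could be judged against the wrong expectation. The Week 24 text, where the sequence costs most, is also where the multiplicity caveat is not repeated.

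**Working it through.** **Inputs.** From protocol Section 9.2 and Tables 5 and 6: 133 participants per arm; 266 against 133 at Week 12 and 133 against 133 at Week 24; two-sided 0.05. Rates (placebo, guselkumab): primary 8%, 22%; Week 12 histologic-endoscopic improvement 8%, 19%; Week 24 endoscopic improvement 13%, 28%; Week 24 clinical remission 10%, 27%.

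**Step 1: reproduce the plan's figures.** With pooled rate p, SE0 = sqrt[p(1−p)(1/n0 + 1/n1)], SE1 = sqrt[p0(1−p0)/n0 + p1(1−p1)/n1], and power = Φ[(p1 − p0 − 1.96·SE0)/SE1].

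- Primary: p = 0.1733, SE0 = 0.0402, SE1 = 0.0346; Φ(1.768) = 96.1%. Stated: above 95%.
- Histologic-endoscopic improvement: p = 0.1533, SE0 = 0.0383, SE1 = 0.0336; Φ(1.040) = 85.1%. Stated: 85%.
- Week 24 endoscopic improvement: p = 0.205, SE0 = 0.0495, SE1 = 0.0486; Φ(1.089) = 86.2%. Stated: 86%.
- Week 24 clinical remission: 95.1%. Stated: 95%.

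The other entries also agree: Week 12 endoscopic improvement 94.0%, and symptomatic remission at both visits and Week 12 clinical response above 99%. Week 24 clinical response comes out above 99.9% where the table prints 99%, which is only rounding.

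**Step 2: the limit set by the sequence.** Confirming q8w endoscopic improvement, or reaching the last endpoint, needs both Week 24 endoscopic tests to be significant, whatever the order inside each block of four. The two tests share the placebo arm, so their correlation is

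0.13×0.87 / (0.13×0.87 + 0.28×0.72) = 0.1131/0.3147 = 0.36.

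| Calculation | Both endoscopic tests significant |
|---|---|
| Independence (0.862 squared) | 74.3% |
| Bivariate normal, correlation 0.36 | 76.4% |
| Binomial counts, shared placebo arm | 78.4% |

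The last two rows are two calculations of one quantity, not a range of uncertainty.

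**Step 3: the test that will be used.** The confirmatory test is the stratified Mantel-Haenszel risk difference with Sato variance, not the chi-square used for sizing. Simulation (200,000 trials per setting) took ADT-IR at 40% to 50% from the plan. It assumed severe endoscopy in 40% to 70%, and rate ratios per stratification factor of 1, 1.4 and 2, because the documents give no stratum rates. Both endoscopic tests succeeded in 78.7–78.8%, 79.2–79.6% and 81.0–81.7% of trials respectively.

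**Step 4: q8w Week 24 clinical remission.** Remission includes the endoscopic criterion ("a rectal bleeding subscore of 0, and an endoscopy subscore of 0 or 1 with no friability present on the endoscopy"), so remission lies inside endoscopic improvement. The correlation between the q4w endoscopic test and the q8w remission test is therefore fixed:

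0.10×0.87 / sqrt(0.3147 × 0.2871) = 0.29, where 0.2871 = 0.10×0.90 + 0.27×0.73.

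The joint probability is 82.8% (normal approximation) or 84.2% (exact) with chi-square. With the stratified test and the settings of Step 3 it is 84.5% to 86.9%. Under the planned test this limit sits at about 85% or above, so by itself it shows no material shortfall for that endpoint.

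**Step 5: the whole sequence.** Chi-square simulation with assumed within-patient correlation from 0 to 0.999 gave about 65% to 78% for q8w endoscopic improvement and 56% to 74% for the last endpoint. These ranges follow the assumed correlation, which the documents do not give.

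**The case for a change.** The strongest case for a change is that the sponsor thought the multiplicity caveat worth stating for Week 12, then left it out of the synopsis and the Week 24 text. Power through the sequence for q8w endoscopic improvement and for the last endpoint is below 85% under the chi-square sizing test and in every stratified setting examined. The correction would be a few words. The SAP Section 3 objective also differs from protocol Section 9.2 on which Week 24 endpoints it covers.

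The calculations behind this case stand, and so does the observation that the qualifier is not repeated. The inference that a figure is overstated does not. In the synopsis, the quoted sentence closes a paragraph that defines power as that of each comparison with placebo by a chi-square test at 0.05, which is individual power. The same synopsis describes the multiplicity-controlled procedure separately. In Section 9.2 the Week 24 sentence follows the Week 12 table and says that power comes from the pairwise comparison, which again is one test at a time. The Amendment 2 entry in Appendix 12 also describes the Week 24 powers added then as individual; it is used here only as evidence of meaning. The narrower clause in SAP Section 3 is a clerical mismatch: the table that follows it gives power for all four Week 24 endpoints.

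**Conclusion.** No change to the plan is needed. The 85% is a correct statement of individual power. It would mislead only if read as the chance of confirmation through the sequence, and neither document says that.

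The cost of the sequence is real but is an ordinary trade-off: every step keeps the full 0.05, and in return late claims depend on earlier ones. Under the stated rates, the limit on q8w Week 24 endoscopic improvement and on the last endpoint is 76% to 78% with the sizing test and about 79% to 82% with the planned stratified test. The second range rests on assumed stratum rates, so a single cap written into the documents would not hold for the confirmatory analysis.

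Nothing in the conduct or analysis turns on the wording. The primary endpoint is tested first at full level with 96.1% power, and protocol Section 9.4.2.2 defines study success by that test alone. Type I error control, the estimands and the estimators are unaffected. Protocol Section 10.6.4 records that recruitment has stopped, so a restated planning power informs no remaining sample size decision. The absent qualifier and the SAP Section 3 clause are editorial, and a statistician following the documents will carry out the right tests in the right order.
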